## 2.2 FAECAL CALPROTECTIN

Given the invasive nature of endoscopy, the implementation of an easy, non-invasive method to support the pre-diagnostic screening and monitoring of disease activity is essential especially in children.

Fecal calprotectin has been shown to be useful in the diagnosis of IBD, correlates with mucosal disease activity and can help to predict response to treatment or relapse. In IBD, the presence of active gut inflammation is associated with migration of leucocytes, including neutrophils, to the gut mucosa. As a result the faecal stream contains increased levels of these inflammatory proteins including calprotectin. Faecal calprotectin has been shown to differentiate quiescent from active disease in both patients with CD and UC.

A meta-analysis including 30 prospective studies showed that the sensitivity and specificity of fecal calprotectin in diagnosing IBDs could reach up to 95% and 91%, respectively. Fecal calprotectin also showed to be a reliable surrogate marker of treatment response. Calprotectin levels decrease significantly after infliximab treatment for 12 weeks, and it correlates with endoscopic index of severity (CDEIS). Røseth et al. (2004) showed that fecal calprotectin levels correlated with endoscopic mucosal healing. A meta-analysis focusing on fecal calprotectin in IBD relapse showed that the sensitivity and specificity when predicting the relapse are 78% and 73%, separately.

Currently, there is limited data on the impact of fecal calprotectin as a marker of treatment response in children. A meta-analysis including 8 pediatric studies (six prospective and two retrospective) showed that pooled sensitivity and specificity for the diagnosis utility of fecal calprotectin during the investigation of suspected pediatric IBD were 0,978 (95%CI,0.947-0.996) and 0,682 (95%CI, 0.502-0.863). Hamalain et al show in 36 children that fecal calprotectin levels rapidly decreases by week 2 in one third of patients treated with infliximab. In a preliminary study Kolho et al measured fecal calprotectin level during the induction and maintenance treatment with infliximab in 76 pediatric patients and concluded that the long-term prognosis was related to the response to induction therapy and reflected in low fecal calprotectin values between weeks 2 and 6 and clinical remission.

## 2.3 THE GEDII REGISTRY

Patient registries are a powerful tool to observe the course of disease, understand variations in treatment and outcomes, to assess effectiveness, to monitor safety and harm and to examine factors that influence prognosis and quality of life. It also allows to describe care patterns and to measure quality of care.

From a clinician's perspective, registries can collect data about disease presentation and outcomes on large numbers of patients rapidly, thereby producing a real-world picture of disease, current treatment practices, and outcomes. A registry might also provide data that can be used to assess the degree to which clinicians are managing a disease in accordance with evidence based guidelines, focus attention on specific aspects of a particular disease that might otherwise be overlooked, or provide data for

clinicians to compare themselves with their peers. Overall, the use of patient registries appears to be active and growing.

The “Grupo de Estudo da Doença Inflamatória Intestinal” (GEDII) Registry was created on 2005 and allows the regular and systematic capture of socio-demographic and clinical characteristics of patients diagnosed with IBDs (CD, UC and indeterminate UC). The Registry also captures the clinical and safety outcomes, treatments and the use of health resources.

So far, the Registry covers 20 gastroenterology departments of public hospitals. As of April 2014, the Registry comprised a total of 2500 patients.

## 2.4 RATIONALE

Thus far, there is limited data on the impact of azathioprine in maintaining fecal calprotectin remission in CD patients.

Taking advantage of the valuable tool such as the GEDII Registry, the GEDII promoted a research to investigate the clinical, biomarker and endoscopic outcomes among patients with Crohn’s disease and managed with azathioprine in the real-world practice. This study will follow a cohort of pediatric patients with Crohn’s disease registered in the GEDII Registry and who are initiating azathioprine, based on physician’s criteria. The cohort will be followed for a period of approximately 2 years.

The primary aim of this study is to explore the potential value of azathioprine in maintaining fecal calprotectin remission in pediatric patients with CD.

## 2.5 RESEARCH HYPOTHESIS

We hypothesize that pediatric Crohn’s disease patients who have induced remission with exclusive polymeric diet, and treated with azathioprine at the diagnosis will maintain fecal calprotectin remission.

## 3 OBJECTIVES

### 3.1 PRIMARY OBJECTIVES

Among patients with Crohn’s disease at study inclusion, registered in the GEDII Registry:

- To evaluate the impact of **azathioprine** in inducing **calprotectin remission** (calprotectin levels < 200 ug/g) at week 12.
- To evaluate the impact of **azathioprine** in maintaining **calprotectin remission** (calprotectin levels < 200 ug/g) at week 48 and 96
- To evaluate the impact of **azathioprine** in maintaining **calprotectin remission** throughout a follow up period of 96 weeks

### 3.2 SECONDARY OBJECTIVES

- To explore the association of the **fecal calprotectin assessment** regarding clinical and endoscopic outcomes.

- To explore the association of **fecal calprotectin** levels with **clinical outcome** throughout a follow up period of 96 weeks.
- To explore the association of **fecal calprotectin** levels with **endoscopic activity** throughout a follow up period of 96 weeks.
- To evaluate the impact of **azathioprine** in inducing clinical remission at week 12.
- To evaluate the impact of **azathioprine** in maintenance of clinical remission up to week 96.
- To evaluate the impact of **azathioprine** in maintaining endoscopic remission at week 96.
- To evaluate the impact of **azathioprine** in maintaining endoscopic remission throughout a follow up period of 96 weeks.
- To evaluate the rate of **azathioprine** persistence throughout a follow up period of 96 weeks
- To evaluate the time until loss clinical remission

## 4 STUDY DESIGN

This is a multicenter, prospective, observational study designed to gather and analyze data on a consecutive cohort of subjects with CD who initiated therapy with azathioprine, according to physician's clinical decision. There is no imposed experimental intervention and prescribing decisions from the study physicians will be independent of patient's participation in this study.

A prospective, observational study is considered an appropriate tool to evaluate the impact of exposures of interest in real-world outcomes and an opportunity to explore biomarkers that can potentially predict clinical response in these settings.

The study will analyze a consecutive sample of 80 patients who are registered in the GEDII Registry and who fulfill the protocol's eligibility criteria. The recruitment period is 12 months but may be extended if the target number of participants is not achieved within the defined timeframe.

The maximum overall duration of observation for each patient is 96 weeks since the start of observation period (Day 1) – see Chronogram in Appendix.

Socio-demographic, clinical and endoscopic data and patterns of use of azathioprine and other therapies for CD will be collected during the observation period, as well as patient reported outcomes (PCDAI). The data collection time points in this study will reflect the routine schedule for CD patients receiving polymeric diet and azathioprine – see Chronogram in Appendix.

The stool samples for assessment of fecal calprotectin will be collected by the patient at home, at the data collection time points.

A total of 11 centers are expected to participate.

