APPENDIX - Chronogram

## 1. Sinopse

Title:	Impact of AZathioprine in maintaining clinical, BIOmarkers and endoscopic remission among new pediatric patients with Crohn's disease treated with exclusive polymeric diet for induction of remission: a 2-year longitudinal analysis from the GEDII Registry – P-BIOAZA
	P-BIOAZA
Scientific Coordinator:	[name]
Disease/Condition	Crohn's disease
Rational	
Thus far, there is limited data on the impact of azathioprine in maintaining fecal calprotectin remission in CD patients.
 
Taking advantage of the valuable tool such as the GEDII Registry, the GEDII promoted a research to investigate the clinical, biomarker and endoscopic outcomes among patients with Crohn's disease and managed with azathioprine in the real-world practice. This study will follow a cohort of pediatric patients with Crohn's disease registered in the GEDII Registry who have induced remission with exclusive polymeric diet and who did initiate azathioprine at diagnosis based on physician's criteria. The cohort will be followed for a period of 2 years.
 
The primary aim of this study is to explore the potential value of azathioprine in maintaining fecal calprotectin remission in pediatric patients with CD.

Research hypothesis:	We hypothesize that pediatric Crohn's disease patients treated with exclusive polymeric diet and with azathioprine at the diagnosis will achieve and maintain fecal calprotectin remission.
Primary Objectives:	
Among patients with Crohn's disease at study inclusion, registered in the GEDII Registry:
 
 
•To evaluate the impact of azathioprine in inducing calprotectin remission (calprotectin levels < 200 ug/g) at week 12.
 
•To evaluate the impact of azathioprine in maintaining calprotectin remission (calprotectin levels < 200 ug/g) at week 48 and 96
 
•To evaluate the impact of azathioprine in maintaining calprotectin remission throughout a follow up period of 96 weeks.
 

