Two recent Cochrane analyses have synthesized the existing data regarding the efficacy of AZA and 6MP in the induction and maintenance of remission in CD. Prefontaine et al. (2010) assessed eight RCTs of AZA/6MP for induction of remission in 425 patients with active CD. Overall response in the pooled treatment group was 54 versus 33% in the placebo arm (odds ratio [OR], 2.43; 95% CI, 1.62-3.64). In addition to clinical response, five studies reported data on corticosteroid reduction while on these agents, with 76 of 117 (65%) thiopurine-treated patients exhibiting reduced steroid use, compared with 39 of 109 (39%) in the placebo group (OR, 3.69; 95% CI, 2.12-6.42). This meta-analysis was updated in 2013, showing that AZA and 6MP offer no advantage over placebo for induction of remission or clinical improvement in active Crohn's disease. However, the combination of AZA and infliximab was superior to infliximab alone for induction of steroid-free remission.

With respect to maintenance of remission, a recent systematic review assessing seven trials with AZA and one with 6MP demonstrated, among 550 adult patients, an OR of 2.32 (95% CI, 1.55-3.49) for AZA and 3.32 (95% CI, 1.40-7.87) for 6MP. A significant number of patients receiving AZA for maintenance of remission had to stop taking the medication due to intolerance, compared with placebo, with an OR of 3.74 (95% CI, 1.48-9.45).

Markowitz et al shown, in 55 children submitted to induction of remission with corticosteroids and randomized to receive 6MP or placebo at week 8, a 9% relapse in the group treated with 6 MP compared with 47% of the controls during a follow up period of 18 months. However subsequent observational studies have not been able to reproduce these low relapse rates, as relapse rates of 40 to 60% were found with azathioprine.

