## 6 STUDY POPULATION

### 6.1 INCLUSION CRITERIA

Study patients must fulfill the following criteria:

1. Male or female patients, <18 years old
2. Patients who are registered in the GEDII Registry;
3. Patients who induce remission with polymeric diet and start azathioprine at diagnosis

**AND** who meet one of the following:

- o Moderate/Severe disease (PCDAI>30) at start of study
- o Mild disease (PCDAI<30) with fecal calprotectin levels > 100 ug/g and/or Endoscopic activity (Simple endoscopic score for Crohn's disease [SES-CD] ≥ 3

4. Patients who gave their informed consent.

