## 9 ENDPOINTS

### 9.1 PRIMARY ENDPOINT

- Proportion of patients who achieve fecal calprotectin remission (< 200 ug/g) at week 12.
- Proportion of patients who maintain fecal calprotectin remission (< 200 ug/g) at week 48 and 96.
- Proportion of patients who maintain fecal calprotectin remission (< 200 ug/g) at each data collection time point up to week 96.

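### The title, objectives and section 4 promise the impact of azathioprine on remission, but a single cohort in which every child starts azathioprine can only describe remission

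*Protocol*

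**What the plan says.** The primary objectives include, in the synopsis, "To evaluate the impact of azathioprine in maintaining calprotectin remission". Section 3.1 repeats this for weeks 48 and 96 and for the whole 96 weeks, and words the week-12 objective on induction the same way. Section 3.2 uses the term again for clinical and endoscopic remission, and the study title opens with it. Section 4 adds that the chosen study type "is considered an appropriate tool to evaluate the impact of exposures of interest in real-world outcomes".

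The rest of the protocol describes one treated cohort. Section 6.1 admits "Patients who induce remission with polymeric diet and start azathioprine at diagnosis"; the synopsis also requires azathioprine to be started at diagnosis. The matching primary endpoint in 9.1 is "Proportion of patients who maintain fecal calprotectin remission (< 200 ug/g) at week 48 and 96". Section 10.1 summarises remission proportions with 95% confidence intervals and uses GEE for a time effect within two subsets defined by disease severity at entry.

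Section 6.3 lists discontinuation of azathioprine among the reasons for ending observation, and says that new Crohn's treatments do not end it while azathioprine continues.

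Section 2.4 is softer: the aim there is to "explore the potential value of azathioprine in maintaining fecal calprotectin remission in pediatric patients with CD".

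**The concern.** The impact of a drug is a contrast between what happened on it and what would have happened without it. The protocol supplies only the first half. If the wording stays, a report that answers the stated objectives will present the proportion in remission at weeks 48 and 96 as something azathioprine achieved, and nothing in the design can support or refute that. The children also receive exclusive polymeric diet, may receive further Crohn's therapy, and are most likely to be seen at week 96 if they stayed on azathioprine.

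This is not a detail to leave to a statistical analysis plan. Eligibility, objectives and the claim of suitability are fixed in the protocol, and later analysis cannot create an unexposed group. Nor can a calprotectin comparator be drawn from routine registry data, since section 7.2 says the registry does not collect calprotectin.

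**Working it through.** **1. The plan's own figure.** Section 10.2 gives one calculation: with 80 patients, more than 95% power that the lower limit of a one-sided 95% interval for a correlation exceeds 0.50 when the correlation is 0.75. By Fisher's z, power = Φ[(atanh 0.75 − atanh 0.50) × √(80 − 3) − 1.645] = Φ[(0.973 − 0.549) × 8.775 − 1.645] = Φ(2.07) = 98.1%. The figure reproduces. It concerns a correlation involving calprotectin and says nothing about an azathioprine effect.

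**2. Is there a contrast anywhere in the plan?**

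| Element | Where | Content | Azathioprine contrast? |
|---|---|---|---|
| Eligibility | Synopsis, 6.1 | All start azathioprine at diagnosis | No |
| Primary endpoints | 9.1 | Proportions of one cohort | No |
| Proportions | 10.1 | 95% intervals, overall and by activity at entry | No |
| GEE | 10.1 | Time effect within severity subsets | No |
| Reference rate or success threshold | 2.5, 9, 10 | None given | No |
| Time off drug | 6.3 | Stopping is a reason to end observation | None planned |

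The two-sample and categorical tests in 10.1 are generic. The only subgroups named there are defined by disease activity or severity at entry, not by exposure.

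**3. What else could produce remission at weeks 48 and 96?** Four explanations compete with azathioprine: lasting benefit of the diet, Crohn's therapy added under 6.3, selection of children who remain on azathioprine and so remain under observation, and disease course. The planned proportions do not separate them.

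**4. Do the background rates in 2.1 supply a reference?** Section 2.1 reports, for a randomised paediatric trial, "a 9% relapse in the group treated with 6 MP compared with 47% of the controls during a follow up period of 18 months", and for later observational studies that "relapse rates of 40 to 60% were found with azathioprine". Taking complements, 100 − 47 = 53% of the trial's controls did not relapse, and 40 to 60% of the azathioprine cohorts did not. Exact (Clopper-Pearson) 95% intervals for maintenance across that range, with 80 evaluable children, are:

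| Maintained | Proportion | 95% interval | Contains 53%? |
|---|---|---|---|
| 32/80 | 40% | 29.2 to 51.6% | No |
| 40/80 | 50% | 38.6 to 61.4% | Yes |
| 48/80 | 60% | 48.4 to 70.8% | Yes |

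Some results would be compatible with the control figure and others would not. Neither outcome would be an estimate of impact. The 53% comes from children induced with corticosteroids and then given placebo, the outcome is relapse rather than calprotectin below 200 ug/g, and the azathioprine cohorts carry no stated follow-up time. The table is an illustration and the finding does not depend on it.

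**The case against.** The strongest reply is that the protocol is open about what it is. It calls itself observational, imposes no intervention, describes its aim as exploratory in 2.4, and plans no analysis that yields a causal estimate. The sentence in section 4 can be read as a general remark about a study type. All of that is fair, and a descriptive cohort is a legitimate design. But the title, the primary objectives and the section 4 statement are what a report will answer, and the softer aim in 2.4 shows that the document is not consistent.

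It may also be said that exposure varies, because dose can be adjusted, is recorded at each visit, and persistence is an endpoint. That is correct as far as it goes: what is missing is an unexposed group, not all variation. However, section 10.1 plans no analysis by dose, and dose here follows the physician's judgement.

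A reader might go further and infer from 2.1 that relapse is much the same with and without a thiopurine, since 47% lies inside 40 to 60%. The document does not support that. The overlap is between studies with different induction and follow-up. The 47% is from placebo controls after corticosteroid induction, so it is neither an untreated rate nor natural history. Within the randomised trial the rates separate clearly, 9% against 47%, and the adult review cited in 2.1 gives an odds ratio of 2.32 (95% CI 1.55 to 3.49) for azathioprine. Nor does the hypothesis in 2.5 set a rate that some result would meet.

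**Conclusion.** The point holds as a mismatch between what the protocol says it will evaluate and what its design can show. Remission at weeks 48 and 96 cannot be attributed to azathioprine, and the same gap applies to the week-12, clinical and endoscopic objectives worded as impact. The conclusion rests on the missing comparator, made harder by added therapy and by observation that can end when the drug stops. It needs no assumption about relapse rates.

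Its consequence is for interpretation: no azathioprine effect, however imprecise, comes out of the planned analysis. The proportions themselves remain estimable, with an interval of about 11 percentage points either side at 50% if all 80 children are evaluable; the protocol gives no dropout rate, and fewer children would widen it. Nothing here says that azathioprine is ineffective, or that the cohort should not be run.

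**What to change.** - **Title, synopsis, 3.1 and 3.2:** reword every azathioprine objective now expressed as impact, including the week-12 and endoscopic ones. The objective becomes to estimate the proportion of children starting azathioprine with exclusive polymeric diet who are in, and who remain in, calprotectin, clinical or endoscopic remission at the stated weeks. The persistence and association objectives can stay.
- **Section 4:** replace the claim that the design evaluates the impact of exposures with a descriptive aim, and state that the cohort supports no causal inference about azathioprine.
- **Section 10.1:** report the remission proportions alongside the data on other Crohn's therapies, which the chronogram already collects at every visit.

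No patient, visit or measurement changes, and no control arm is asked for. The cost is an amendment of wording, one further tabulation, and a more modest stated conclusion.

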## 5 STUDY TIMELINES

The study is expected to start during the 2nd Quarter of 2016.

The overall duration of the study is approximately three years (1 year of recruitment + 2-year observation period).

## 6 STUDY POPULATION

### 6.1 INCLUSION CRITERIA

Study patients must fulfill the following criteria:

1. Male or female patients, <18 years old
2. Patients who are registered in the GEDII Registry;
3. Patients who induce remission with polymeric diet and start azathioprine at diagnosis

**AND** who meet one of the following:

- o Moderate/Severe disease (PCDAI>30) at start of study
- o Mild disease (PCDAI<30) with fecal calprotectin levels > 100 ug/g and/or Endoscopic activity (Simple endoscopic score for Crohn's disease [SES-CD] ≥ 3

4. Patients who gave their informed consent.

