Secondary Objective(s):	
 
•To explore the association of the fecal calprotectin assessment regarding clinical and endoscopic outcomes.
 
•To explore the association of fecal calprotectin levels with clinical outcome throughout a follow up period of 96 weeks.
 
•To explore the association of fecal calprotectin levels with endoscopic activity throughout a follow up period of 96 weeks.
 
•To evaluate the impact of azathioprine in inducing clinical remission at week 12.
 
•Among patients who achieve clinical remission with azathioprine, to evaluate the maintenance of clinical remission up to week 96.
 
•To evaluate the impact of azathioprine in inducing endoscopic remission at week 96.
 
•To evaluate the impact of azathioprine in maintaining endoscopic remission throughout a follow up period of 96 weeks.
 
•To evaluate the rate of azathioprine persistence throughout a follow up period of 96 weeks
 

	
 
•To evaluate the time until loss clinical remission
 

Study Design:	
Multicenter, prospective, observational study designed to gather and analyze data on a consecutive cohort of subjects with CD who initiated therapy with azathioprine, according to physician's clinical decision. There is no imposed experimental intervention and prescribing decisions from the study physicians will be independent of patient's participation in this study.
 
The maximum overall duration of observation for each patient is 96 weeks since the start of observation period (Day 1).

Inclusion Criteria:	
Study patients must fulfill the following criteria:
 
 
1. Male or female patients, <18 years;
 
2. Patients who are registered in the GEDII Registry;
 
3. Patients who have been treated with exclusive polymeric diet and start azathioprine at diagnosis
 
 
AND who meet one of the following:
 
 
o Moderate/Severe disease (PCDAI>31) at start of study with fecal calprotectin levels > 100 ug/g
 
o Mild disease (PCDAI>11<30) with fecal calprotectin levels > 100 ug/g and/or Endoscopic activity (Simple endoscopic score for Crohn's disease [SES-CD] ≥ 3)
 
 
 
4. Patients who gave their informed consent.
 

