The initial therapy available for the acute management of CD has traditionally been systemic corticosteroids. Several early studies demonstrated the efficacy of corticosteroids in inducing remission in CD, with remission rates in up to 92% of patients. Despite the ability to induce remission, corticosteroids have not demonstrated equivalent efficacy at maintaining remission and are also known for relevant long-term side effects. Exclusive polymeric diet has a similar rate of induction of remission as corticosteroids and has no side effects. For that reason exclusive polymeric diet is considered the first line therapy to induce remission in children with active luminal disease usually in association with azathioprine for maintenance of remission. Thiopurines are recommended as one option for maintenance of steroid free remission in children at risk of poor disease outcome. Thiopurines alone are not recommended as induction therapy. When exclusive polymeric diet is not an option corticosteroids may be necessary. There are two main classes of corticosteroid-sparing agents and in moderate to severe CD: the immunomodulators, which include azathioprine (AZA), 6-mercaptopurine (6MP), and methotrexate (MTX), and the newer "biologics," monoclonal antibodies against TNF- $\alpha$ , which include infliximab, adalimumab, and certolizumab pegol. In addition, there has been recent evidence suggesting that combination therapy with an immunomodulator and biologic may be the most efficacious and may potentially alter the underlying prognosis of CD.

The thiopurines, which consist of AZA and 6MP, exert their effect via inhibition of purine synthesis. AZA is a prodrug, converted to 6MP within the host. AZA and 6MP dosing must be carefully titrated due to potential marrow-suppressive and hepatotoxic effects. The goal dose of AZA is typically

between 2 to 3 mg/kg/day, whereas the dose for 6MP is half this, at 1 to 1.5 mg/kg/d. As specific metabolites can lead to undesirable side effects, it is advisable to measure TPMT genotype or enzymatic activity prior to initiation of therapy. A rare TPMT genetic variant, for which ~0.3% of individuals are homozygous, can result in decreased TPMT function and elevated levels of 6-TG resulting in life-threatening marrow suppression. Approximately 11% of individuals are heterozygotes for this codominant mutation, requiring reduced dosing.

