#### Basal characteristics

- Date of birth
- Sex
- Height
- Weight
- BMI
- Smoking status
- Diagnosis of CD and date

- Date of start of symptoms
- Familial history of IBDs
- Disease presentation (abdominal, constitutional, abdominal + constitutional, anal disease, acute abdomen, fever, anemia, extra-intestinal manifestation, abdominal mass, similar presentation to UC, growth failure)
- Clinical course
- PDAI includes (CD activity): Subjective reporting of the degree of abdominal pain; Presence of extraintestinal manifestations, such as fever, arthritis, rash, and uveitis; Physical examination findings; Weight and height; Hematocrit, erythrocyte sedimentation rate, and serum albumin.  
The scale can be assessed at: [http://www.gedii.pt/\\_scores\\_online](http://www.gedii.pt/_scores_online)
- Routine laboratory parameters (hemoglobin, leukocytes, neutrophils, eosinophiles, basophiles, monocytes, lymphocytes, erythrocyte sedimentation rate, CRP, ferritin, iron and transferrin)
- First episode - Paris classification for CD: age at diagnosis, location, behavior, growth.  
The scale can be assessed at: [http://www.gedii.pt/\\_scores\\_online](http://www.gedii.pt/_scores_online)
- Anal lesion (strictures, abscesses, or fistulas)
- Extra-abdominal manifestations
- Colonoscopy - Simple endoscopic score for Crohn's disease (SES-CD)  
The scale can be assessed at: [http://www.gedii.pt/\\_scores\\_online](http://www.gedii.pt/_scores_online)
- Dose of azathioprine, date of start (Day 1)
- Concomitant therapies (from Day 1)
- Stool sampling - assessment of fecal calprotectin levels:
  - The stools will be sent to a central lab (Departamento de Farmacologia Faculdade Medicina do Porto)
  - Calprotectin testing – sample sent to central laboratory

**Information to be collected at each data collection time points of follow up (every 12 weeks up to week 96) – see Chronogram.**

- Weight/ Height/BMI
- Dose of azathioprine, if changed since previous data collection time point.
- Concomitant therapies (including CD therapies), if changed since previous data collection time point.
- Clinical activity ( PDAI)
- Routine laboratory parameters (hemoglobin, leukocytes, neutrophils, eosinophiles, basophiles, monocytes, lymphocytes, erythrocyte sedimentation rate, CRP, ferritin, iron and transferrin)
- Stool sampling - assessment of fecal calprotectin levels:

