#### **Observation period**

- Start of observation period – corresponds to the date of the first appointment of the study
- End observation period – 96 weeks after the basal assessment

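### Section 6.1 and the synopsis disagree on whether remission on diet is an entry condition, and the first primary objective credits azathioprine with a week-12 induction that this single-cohort design cannot attribute to it

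*Protocol*

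**What the plan says.** **Entry.** Criterion 3 of section 6.1 reads "Patients who induce remission with polymeric diet and start azathioprine at diagnosis". It is joined by AND to one of two activity conditions: "Moderate/Severe disease (PCDAI>30) at start of study", or "Mild disease (PCDAI<30) with fecal calprotectin levels > 100 ug/g and/or Endoscopic activity" (SES-CD of 3 or more). The same criterion in the synopsis reads "Patients who have been treated with exclusive polymeric diet and start azathioprine at diagnosis", and the synopsis mild branch has a lower PCDAI limit of 11. The synopsis rationale and section 2.5 describe patients whose remission has already been induced by diet. The synopsis hypothesis instead expects treated patients to go on to achieve remission and keep it.

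**Remission.** Section 9.3 defines clinical remission as PCDAI below 10 (the synopsis endpoint uses 10 or below). Section 6.1 does not say whether the remission on diet is clinical or by calprotectin, or when it is assessed.

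**Time origin.** Section 7.1 lists "Dose of azathioprine, date of start (Day 1") among the baseline items. Section 4 equates Day 1 with the start of observation, which section 9.3 says "corresponds to the date of the first appointment of the study".

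**First primary objective.** Section 3.1 and the synopsis ask for the effect of azathioprine on inducing calprotectin remission (below 200 ug/g) at week 12. The matching endpoint in section 9.1 is a single proportion. Section 2.1 says "Thiopurines alone are not recommended as induction therapy" and, citing a 2013 meta-analysis update, that "AZA and 6MP offer no advantage over placebo for induction of remission".

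**The concern.** Two things are at stake.

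The first is who is enrolled. One set of words admits every child given the diet with azathioprine at diagnosis; the other admits only those in whom the diet worked. With about 11 centres applying the criteria, both populations could enter. If responders alone are kept, a result that arises after treatment starts has been used as a baseline condition, and the week-12 rate no longer describes children who start this treatment.

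The second is what may be concluded. The objective names azathioprine as the agent that induces remission. The protocol's own background and its section 2.5 hypothesis give induction to the diet and maintenance to azathioprine. A favourable week-12 proportion, reported against the objective as written, would carry a causal claim that the design does not support.

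**Working it through.** **The plan's own figure.** Section 10.2 states power above 95% with N = 80 for a one-sided 95% lower limit above 0.50 when the correlation is 0.75. By Fisher's z:

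- atanh(0.75) = 0.973; atanh(0.50) = 0.549; difference 0.424
- 0.424 × √(80 − 3) = 3.72; 3.72 − 1.645 = 2.07
- Φ(2.07) = 98.1%

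The statement reproduces, but it concerns a correlation and says nothing about the week-12 objective.

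**Entry criteria, taking remission as clinical (PCDAI below 10).**

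| When activity is read | PCDAI > 30 branch of 6.1 | Mild branch of 6.1 (PCDAI < 30) |
|---|---|---|
| After the remission on diet | Cannot be met: below 10 and above 30 exclude each other | Can be met, e.g. PCDAI below 10 with calprotectin above 100 ug/g |
| At diagnosis, before the diet has acted | Can be met, but entry then depends on a later response | Can be met, with the same dependence |

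In the first row the moderate/severe subset would be empty, although sections 9.2 and 10.1 plan analyses in it. In the second row, diet non-responders drop out of the cohort by definition. With the synopsis criterion neither problem arises. The synopsis mild branch (PCDAI above 11) would also exclude a patient already in clinical remission.

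**Effect of selecting responders.** Let f be the share not reaching remission on diet, and pR and pN the week-12 calprotectin remission rates in responders and non-responders.

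- All treated: (1 − f)·pR + f·pN
- Responders only: pR
- Difference: f·(pR − pN)

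The direction is upward whenever pR exceeds pN. The protocol gives none of the three inputs for this population. Assumed values of pR = 60% and pN = 10% show how far the answer moves with f alone:

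- f = 8%: 0.92 × 0.60 + 0.08 × 0.10 = 56%, difference 4 points
- f = 20%: 0.80 × 0.60 + 0.20 × 0.10 = 50%, difference 10 points
- f = 40%: 0.60 × 0.60 + 0.40 × 0.10 = 40%, difference 20 points

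The 8% is the complement of the rate of up to 92% that section 2.1 cites for corticosteroids, to which it likens the diet. It is a best case.

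**Attribution at week 12.** Section 4 describes one cohort, all starting azathioprine; criterion 3 gives all of them the diet. Exposure to either treatment does not vary between patients, so the week-12 proportion reflects diet, azathioprine and natural course together. It can still be described. Wilson 95% intervals at N = 80 (observed rates assumed) are:

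- 40%: 30.0% to 51.0%
- 60%: 49.0% to 70.0%
- 80%: 70.0% to 87.3%

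A larger sample would narrow these intervals but would not separate the two treatments.

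**The case against.** The strongest reply is that inducing remission with the diet is loose wording for receiving the diet as induction therapy. The study title, the synopsis criterion and the synopsis hypothesis fit that reading. Active disease at the start is then consistent with entry, and no responders are selected. This is plausible and may be what was meant, but the synopsis rationale and section 2.5 speak of remission already induced, so the text needs to settle it. The reply also leaves the attribution problem untouched.

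A second reply is that the study is openly observational, its stated aim is exploratory, and the endpoint is a proportion with a confidence interval. That stands: no comparative test is planned and the proportion is estimable. The fault lies in the objective's wording, not in the endpoint.

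Three stronger readings are tempting and should be resisted.

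- *Day 1 has two different dates.* Section 9.3 does not place the first appointment after the diet. Section 6.1 starts azathioprine at diagnosis, section 7.1 lists its start among the baseline items, and the Chronogram puts disease presentation, colonoscopy and azathioprine dose on Day 1. These point to one date. The protocol does not say that the dates coincide, which calls for a clarification; no shift of the week-12 clock is shown.
- *Section 6.1 is contradictory throughout.* Only the PCDAI above 30 branch conflicts outright, and only if remission is clinical and precedes the activity reading.
- *The week-12 rate is inflated by 10 to 20 points.* That rests on assumed rates, and the one rate section 2.1 offers gives about 4 points with the same response assumptions.

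**Conclusion.** The point holds in two parts.

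First, the protocol contradicts itself on whether remission on diet is an entry condition. On the literal reading, section 6.1 either empties its moderate/severe branch or conditions entry on a later response. The first consequence assumes that the remission meant is clinical. The second would be expected to raise the week-12 rate, assuming responders do better on calprotectin than non-responders; its size cannot be derived from the protocol.

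Second, the first primary objective cannot be answered as worded, because nothing in the design separates azathioprine from diet at week 12 and the protocol's own background argues against azathioprine as the inducing agent. This holds whichever entry reading is adopted. A reader might infer that the week-12 result is worthless. It is not: it remains a valid description of remission after the combined treatment, with a half-width of roughly 10 points at N = 80 and a rate near 60%.

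Entry criteria and a primary objective are protocol matters and should be corrected in the protocol itself.

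**What to change.** 1. Make the synopsis rationale, the synopsis criterion, section 2.5 and section 6.1 agree by using the synopsis criterion: treated with exclusive polymeric diet and started on azathioprine at diagnosis, whatever the result of the diet. State that activity is measured at Day 1, before the response to diet is known.
2. Reword the first primary objective as describing the proportion in calprotectin remission at week 12 after exclusive polymeric diet plus azathioprine.
3. Report maintenance at weeks 48 and 96 as a single-arm description among patients in calprotectin remission at week 12, and drop the word *impact*. Maintenance has no comparator either.
4. As a clarification in sections 4, 7.1 and 9.3, state that Day 1 is both the azathioprine start date and the baseline visit.

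The cost is a wording amendment with no new data: the Chronogram already schedules PCDAI, SES-CD and a stool sample on Day 1. The price is a narrower claim, possibly a less favourable week-12 rate, and a smaller maintenance denominator. At assumed week-12 rates of 40% to 60%, that denominator would be 0.40 × 80 = 32 to 0.60 × 80 = 48 patients before any drop-out.
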